3.4.1. Stratification Factor

Participants will be stratified by disease severity as measured by baseline IGA score (3 [moderate AD], 4 [severe AD]). The stratum derived from data collected on IGA score at baseline will be used for all analyses requiring this stratification variable (Section 5.2). This stratification is called the actual IGA stratification variable. The stratum of IGA score reported to the randomization system is called the reported IGA stratification.

For the primary endpoint of IGA response at Week 16 in Part 1 DB phase, a sensitivity analysis will be performed using the reported IGA stratification if there are discrepancies between the actual IGA stratification and the reported IGA stratification. A participant listing will be provided comparing the reported IGA stratification variable (to the randomization system) and actual IGA stratification variable (derived using the clinical database).

3.5. Safety Endpoints

All the safety data will be summarized descriptively through appropriate data tabulations, descriptive statistics, and graphical presentations. Treatment-emergent AEs including SAEs and AE leading to discontinuation of study treatment, vital signs, 12-lead ECG parameters, and laboratory tests, etc. will be summarized according to the Clinical Data Interchange Standards Consortium (CDISC) and Pfizer Standards (CaPS). Treatment-emergent AE is defined as an AE that started on or after the first dose of study treatment (ie, baseline, without regard to baseline severity). The MedDRA version for AE coding at the time of database release will be adopted and the version used will be displayed in all relevant safety data tabulations. All safety analyses will be performed on the SAS (Section 4.2).

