Interactions with other medicinal products and other forms of interaction	Based on data from CYP-mediated clinical drug interaction studies, moderate increases in exposure of etrasimod were observed when multiple CYPs were inhibited (fluconazole) or decreased when multiple CYPs were induced (rifampin). Thus, the use of moderate or strong inhibitors or inducers that inhibit or induce at least 2 of the following is not recommended: cytochrome P450 CYP2C8, CYP2C9, and CYP3A4.	To minimize potential DDI, drugs known to inhibit or induce the following cytochrome P450 enzymes, CYP2C8, CYP2C9, and CYP3A4 are prohibited within 4 weeks prior to baseline (Day 1): • Moderate to strong inducers/inhibitors of two or more of the CYP enzymes above (eg, fluconazole)
	Caution should be used during concomitant administration of immunomodulatory or immunosuppressive therapies with etrasimod due to the risk of additive immune effects during such therapy and in the weeks following administration.	To minimize the risk of additive immune effects during the study, mandatory washout periods for immune-modulating and immunosuppressive therapies will be implemented as described in Section 6.9.2.
Study Procedures		
Worsening of AD	Participants discontinuing their AD treatment during the washout period may experience the worsening of their AD symptoms.	Participants may discontinue treatment or withdraw from the study at any time for any reason.
	A worsening of AD may occur during the treatment period and follow-up period.	Participants meeting withdrawal/discontinuation criteria (Section 7.2) may be able to use alternative treatments after withdrawal from the study.

Potential Risk of Clinical Significance	Summary of Data/Rationale for Risk.	Mitigation Strategy
		Participants will be assessed for safety at regular intervals throughout the study to identify and mitigate the risks the potential risks.
Other		
The COVID-19 pandemic/regional emergency situations may pose risks to study participation	Participants may be at increased safety risk by attending a clinic visit.	Use of telehealth and/or home health visits will be utilized in the study to minimize potential exposure of trial participants to emergency situations (Section 8.1.2 and Section 8.1.3).

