8.4.1. Time Period and Frequency for Collecting AE and SAE Information

The time period for actively eliciting and collecting AEs and SAEs ("active collection period") for each participant begins from the time the participant provides informed consent, which is obtained before undergoing any study-related procedure and/or receiving study intervention, through and including a minimum of 4 weeks after the last administration of the study intervention.

Follow-up by the investigator continues throughout the active collection period and until the AE or SAE or its sequelae resolve or stabilize at a level acceptable to the investigator.

When a clinically important AE remains ongoing at the end of the active collection period, follow-up by the investigator continues until the AE or SAE or its sequelae resolve or stabilize at a level acceptable to the investigator and Pfizer concurs with that assessment.

For participants who are screen failures, the active collection period ends when screen failure status is determined.

If the participant withdraws from the study and also withdraws consent for the collection of future information, the active collection period ends when consent is withdrawn.

If a participant permanently discontinues or temporarily discontinues study intervention because of an AE or SAE, the AE or SAE must be recorded on the CRF and the SAE reported using the CT SAE Report Form.

Investigators are not obligated to actively seek information on AEs or SAEs after the participant has concluded study participation. However, if the investigator learns of any SAE, including a death, at any time after a participant has concluded study participation, and they consider the event to be reasonably related to the study intervention, the investigator must promptly report the SAE to Pfizer using the CT SAE Report Form.

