- Alternative causes, such as underlying disease(s), concomitant therapy, and other risk factors, as well as the temporal relationship of the event to study intervention administration, will be considered and investigated.

- The investigator will also consult the IB and/or product information, for marketed products, in their assessment.
- For each AE or SAE, the investigator must document in the medical notes that they have reviewed the AE or SAE and have provided an assessment of causality.
- There may be situations in which an SAE has occurred and the investigator has minimal information to include in the initial report to the sponsor. However, it is very important that the investigator always make an assessment of causality for every event before the initial transmission of the SAE data to the sponsor.
- The investigator may change their opinion of causality in light of follow-up information and send an SAE follow-up report with the updated causality assessment.
- The causality assessment is one of the criteria used when determining regulatory reporting requirements.
- If the investigator does not know whether or not the study intervention caused the event, then the event will be handled as "related to study intervention" for reporting purposes, as defined by the sponsor. In addition, if the investigator determines that an SAE is associated with study procedures, the investigator must record this causal relationship in the source documents and CRF, and report such an assessment in the dedicated section of the CT SAE Report Form/PSSA and in accordance with the SAE reporting requirements.

Follow-Up of AEs and SAEs

- The investigator is obligated to perform or arrange for the conduct of supplemental measurements and/or evaluations, as medically indicated or as requested by the sponsor, to elucidate the nature and/or causality of the AE or SAE as fully as possible. This may include additional laboratory tests or investigations, histopathological examinations, or consultation with other healthcare providers.
- If a participant dies during participation in the study or during a recognized follow-up period, the investigator will provide Pfizer Safety with a copy of any postmortem findings, including histopathology.
- New or updated information will be recorded in the originally submitted documents.
- The investigator will submit any updated SAE data to the sponsor within 24 hours of receipt of the information.

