3. ENDPOINTS AND BASELINE VARIABLES: DEFINITIONS AND CONVENTIONS

3.1. Primary Endpoints

For Part 1 DB,

• IGA response at Week 16.

IGA response is defined as clear (0) or almost clear (1) on a 5-point scale and a reduction of ≥ 2 points from baseline (Appendix 2.2.1). Only participants with baseline IGA ≥ 2 in the FAS are included in all analyses of IGA response.

For Part 1 OLE and Part 2,

- Incidence and severity of treatment-emergent AEs, AEs leading to study treatment discontinuation, SAEs, and AESIs.
- Incidence of clinically significant changes in clinical laboratory values, ECG measurements and vital signs.

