3.5.1. Adverse Events (Including Laboratory Data)

In this study, the safety endpoints included in safety data summaries are listed in, although not limited to, the following:

- Incidence and severity of treatment-emergent AEs, AE leading to study treatment discontinuation, SAEs, and AESI, etc.
- Incidence of clinically significant changes in clinical laboratory values, 12-lead ECG measurements, and vital signs, etc.
- Change from baseline in laboratory values (hematology, serum chemistry, coagulation, and urinalysis), 12-lead ECG measurement, vital signs, and other objective safety measures.

These safety endpoints are considered as primary endpoints for the Part 1 OLE and Part 2 OL Safety phases. Definitions of baseline for Part 1 and Part 2 are previously provided (Section 3.4).

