3.5.2. Adverse Events of Special Interest

Treatment-emergent AESIs are identified per study protocol and require close monitoring. All AESIs must be reported as an AE or SAE following the reporting procedures described in

the protocol. An AESI that is also an SAE must also be reported using the CT SAE Report Form. The following are AESI identified for etrasimod (except for PML, the MedDRA search terms for AESI are recorded in a separate charter for the etrasimod clinical program):

- Cardiovascular events (eg, bradycardia, AV conduction delay, and hypertension);
- Macular oedema*;
- Pulmonary events (airflow obstruction or altered gas exchange);
- Infections (severe infections, opportunistic infections including PML*, herpes simplex and herpes zoster);
- Liver injury (liver transaminase elevation and bilirubin elevation);
- PRES*; and
- Malignancies*.
- * A diagnosis of this event requires permanent discontinuation of study intervention.

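### SAP 3.5 defines treatment-emergent AEs by start date alone, so a screening-onset AE that worsens on drug drops out of the TEAE and AESI summaries if the worsening stays on its original record

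*SAP*

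**What the plan says.** SAP 3.5 gives the only definition of treatment emergence in either document: "Treatment-emergent AE is defined as an AE that started on or after the first dose of study treatment (ie, baseline, without regard to baseline severity". Although the Protocol uses the term in its endpoints, it does not define it.

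For the Part 1 OLE and Part 2, SAP 3.1 lists the endpoint as "Incidence and severity of treatment-emergent AEs, AEs leading to study treatment discontinuation, SAEs, and AESIs", and SAP 3.5.1 confirms its rank: "These safety endpoints are considered as primary endpoints for the Part 1 OLE and Part 2 OL Safety phases". Elsewhere the SAP puts the other components under the same heading. SAP 3.5, repeated in 6.5, writes "Treatment-emergent AEs including SAEs and AE leading to discontinuation of study treatment", and SAP 3.5.2 opens with "Treatment-emergent AESIs are identified per study protocol and require close monitoring". SAP 6.5.1 says that the standard displays tabulate treatment-emergent AEs.

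On data collection, Protocol 8.4.1 says that the active period "begins from the time the participant provides informed consent", and the Schedule of Activities allows up to 28 days of screening before Day 1. On updates to an existing event, Protocol 10.3.3 says: "New or updated information will be recorded in the originally submitted documents".

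**The concern.** The database will be able to hold AEs that started in screening and are still ongoing at the first dose. If such an event becomes more severe or serious on etrasimod, a safety summary should show it, because the change happened under exposure. The definition looks only at when the event began. If the worsening is entered as an update to the existing record, the start date stays before dosing and the event fails the definition.

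The affected summaries are primary in Part 2, which has one arm and exists to build the safety database, so no control group helps a reader judge what is missing. The AESI list includes infections and liver injury, both of which can start mildly and progress. Eligibility leaves room for this: the exclusions in Protocol 5.2 cover active uncontrolled infection and transaminases at or above 2 × ULN, but not every mild infection or raised value below that limit. Protocol 10.5 sets separate thresholds for participants whose liver values are already abnormal at baseline, so the Protocol itself treats worsening from an abnormal start as a safety signal.

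**Working it through.** The plan states no figure that depends on this definition, so there is nothing to reproduce. The check is on the text.

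**Step 1. Is there a worsening clause anywhere?** SAP 3.1, 3.5, 3.5.1, 3.5.2, 5.3, 6.5.1 and Appendix 2.1 were read against Protocol 8.4.1, 9.3.5 and 10.3.1 to 10.3.3. None adds events that start before the first dose and then increase in severity or become serious.

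**Step 2. Does the documents' recording rule settle the matter?** Two provisions bear on it.
- Protocol 10.3.1 makes an exacerbation of a chronic or intermittent preexisting condition an AE, and its general definition covers exacerbated as well as new disease. This supports opening a new record.
- Protocol 10.3.3 sends new or updated information to the original documents. This supports updating the old record.

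Neither says which applies to an acute event already logged as an AE during screening.

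**Step 3. Follow one hypothetical event by both routes.** A mild infection starts on Day -6, is ongoing at Day 1, and leads to hospitalisation on Day 12. Assume that it falls within the AESI search terms.

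| | New record, start Day 12 | Original record updated, start Day -6 |
|---|---|---|
| TEAE under SAP 3.5 | Counted | Not counted |
| Treatment-emergent AESI under SAP 3.5.2 | Counted | Not counted |
| SAE, read from the endpoint list in SAP 3.1 | Counted | Counted |
| SAE, read from SAP 3.5 and 6.5 | Counted | Not counted |

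The same clinical course gives different results in three of the four rows, depending on how the site records it.

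**Step 4. How many participants?** The documents give no rate of AEs ongoing at first dose and no rate of worsening. As an assumption only, let 10% to 20% of participants have an AE ongoing at first dose, and let 5% to 10% of those worsen on treatment:
- low: 0.10 × 0.05 = 0.005, or 0.5%; high: 0.20 × 0.10 = 0.02, or 2%
- Part 2 (about 340 participants): 0.005 × 340 = 1.7 to 0.02 × 340 = 6.8
- Part 1 (about 60 participants): 0.005 × 60 = 0.3 to 0.02 × 60 = 1.2

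A wider assumption of 1% to 5% of Part 2 participants gives 0.01 × 340 = 3.4 to 0.05 × 340 = 17. These counts cover worsening of any AE, minor or not, and assume that every worsening stays on the old record. A participant with another TEAE still counts in overall TEAE incidence, but the worsened event is missing from its own row and from the severity summary.

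**The case against.** The strongest reply is that exclusion is not established. The 10.3.3 sentence sits among follow-up instructions and is not a rule about onset dates. Protocol 10.1.7 leaves CRF completion guidance to a separate document, and AE summaries follow sponsor standards; neither is available here, and either may tell sites to open a new record. Under Protocol 10.3.1 a site could properly do so, and SAP 3.5 would then count the event. This stands, and it limits the finding to worsening that stays on the original record.

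Second, a hospitalised case is an SAE, and the endpoint names SAEs and AEs leading to discontinuation as components of their own. A reader might infer that such a case vanishes from the SAE count. The documents do not support that: they conflict, and the fair description is ambiguity. The SAE would also reach the sponsor within 24 hours (Protocol 8.4.1.1), and the E-DMC monitors safety throughout. Those safeguards protect participants but do not settle what the tables contain.

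Third, Protocol 2.3.1 says "Participants discontinuing their AD treatment during the washout period may experience the worsening of their AD symptoms". This might be taken as evidence that AEs will be ongoing at Day 1. It is weak support, because Protocol 10.3.1 excludes signs of the disease under study unless they are more severe than expected.

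Fourth, the remark about baseline severity can be read as inclusive: any AE starting after dosing counts, even where the condition was equally severe before. That may add events, so the net direction of the whole definition is not shown. It does not bring back an event with a pre-dose start, because the start-date condition still applies.

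**Conclusion.** The point holds in limited form. SAP 3.5 classifies by start date, has no worsening clause, and leaves inclusion of a screening-onset AE that worsens on drug to how the site records it. When the worsening stays on the original record, the event is left out of the TEAE and treatment-emergent AESI summaries. Its place in the SAE count is unresolved.

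The effect falls mainly on Part 2, where screening leads directly into etrasimod and the summaries are primary. The number affected cannot be derived from the documents and is probably small; the range of about 2 to 7 of 340 rests wholly on assumed rates. All safety analysis is descriptive, so no test or error rate is involved.

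Two further inferences should not be drawn. A percentage understatement of serious or AESI infection rates cannot be given, because it would divide worsenings of any AE by a rate of a much narrower kind of event, with no source for either. Nor does this defect call for a separate rule at the first open-label dose in Part 1: an AE that starts in the double-blind phase already follows the first dose and is a TEAE.

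The change should be made before database release. It corrects a stated rule behind a primary endpoint at very low cost.

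**What to change.** 1. In SAP 3.5, define a TEAE as an AE that starts on or after the first dose, or that starts before the first dose and increases in severity or becomes serious on or after it.
2. In Protocol 10.3.3 or the CRF completion guidance, state that worsening of an AE ongoing at first dose is recorded with its own date, either as a new record or as a dated change in severity. Without that date the new clause cannot be applied.
3. In SAP 3.5 and 6.5, state that the counts of SAEs and of AEs leading to discontinuation include such events, so that these sections agree with SAP 3.1.

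The cost is one SAP clause, one recording instruction and one clarifying sentence, plus a few more AE records and a slightly higher TEAE count.

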3.5.1. Adverse Events (Including Laboratory Data)

In this study, the safety endpoints included in safety data summaries are listed in, although not limited to, the following:

- Incidence and severity of treatment-emergent AEs, AE leading to study treatment discontinuation, SAEs, and AESI, etc.
- Incidence of clinically significant changes in clinical laboratory values, 12-lead ECG measurements, and vital signs, etc.
- Change from baseline in laboratory values (hematology, serum chemistry, coagulation, and urinalysis), 12-lead ECG measurement, vital signs, and other objective safety measures.

These safety endpoints are considered as primary endpoints for the Part 1 OLE and Part 2 OL Safety phases. Definitions of baseline for Part 1 and Part 2 are previously provided (Section 3.4).

3.5.2. Adverse Events of Special Interest

Treatment-emergent AESIs are identified per study protocol and require close monitoring. All AESIs must be reported as an AE or SAE following the reporting procedures described in

the protocol. An AESI that is also an SAE must also be reported using the CT SAE Report Form. The following are AESI identified for etrasimod (except for PML, the MedDRA search terms for AESI are recorded in a separate charter for the etrasimod clinical program):

- Cardiovascular events (eg, bradycardia, AV conduction delay, and hypertension);
- Macular oedema*;
- Pulmonary events (airflow obstruction or altered gas exchange);
- Infections (severe infections, opportunistic infections including PML*, herpes simplex and herpes zoster);
- Liver injury (liver transaminase elevation and bilirubin elevation);
- PRES*; and
- Malignancies*.
- * A diagnosis of this event requires permanent discontinuation of study intervention.

3.5.3. Study Treatment Compliance

In addition to safety endpoints, the study treatment compliance (%) will be derived from the total number of doses actually taken divided by the total number of doses expected to take between two scheduled visits using dosing data collected in the Treatment Dosing CRF page. Compliance is expressed in percentage. Both the randomized treatments (ie, etrasimod 2 mg QD and placebo) will be taken into account. Participants who have study treatment compliance of <80% or >120% between two scheduled visits will be identified in a listing.

4. ANALYSIS SETS (POPULATIONS FOR ANALYSIS)

Data for all participants will be assessed to determine if participants meet the criteria for inclusion in each analysis set (population) prior to unblinding, releasing the database for analyses. Classification of participants to analysis sets will be documented per standard operating procedures. For participants with multiple enrollments, only the participant identifier and data under initial enrollment will be included and summarized. Data collected for other enrollments with be included only in listings and narratives.

Participants who are screened but do not meet inclusion criteria or meet exclusion criteria to enter the study (ie, screen failure), they will be counted as a single group and this is how far they are summarized (Section 6.4.2). Below are descriptions of the analysis sets defined for this study.

4.1. Full Analysis Sets

The full analysis set (FAS) will include all participants who are randomized to the study irrespective of whether they receive any dose of study intervention (ie, etrasimod or placebo). Participants will be analyzed in the treatment groups as they are randomized. If a participant DMB02-GSOP-RF02 7.0 Statistical Analysis Plan Template 31-Jan-2022

is treated but not randomized, then this participant will be excluded from the FAS. A narrative will be provided for this participant in the clinical study report (CSR). For a participant who is randomized but not treated, for Part 1 DB and OLE, baseline value for efficacy and safety endpoints is defined as the value obtained on the date of randomization as Day 1 or prior (if the Day 1 value is not available) in the Part 1 DB phase in the analyses.

In general, the analysis population for analyzing all efficacy endpoints in this study is defined by the complete FAS. However, there are some exceptions: some efficacy endpoints, defined by specific point reduction from baseline, require the inclusion of only participants who meet a baseline threshold in the analysis set to allow them the potential to respond in these efficacy endpoints. The details of these exceptions are provided below. Therefore, when considering analyzing an efficacy endpoint under an estimand, it is important to consider these exceptions.

FAS for Specific Efficacy Endpoints

The following four binary efficacy endpoints will only be analyzed including participants who meet the specific baseline threshold. This is to ensure that only participants with the potential to respond at a post-baseline visit are included in the analyses.

- IGA response defined as clear (0) or almost clear (1) on a 5-point scale and a reduction of ≥2 points from baseline (Appendix 2.2.1): Only participants with baseline IGA ≥2 in the FAS are included in all analyses of IGA response, knowing that only participants with baseline IGA ≥3 are eligible to enroll in this study.
- ≥4-point reduction in PP-NRS score from baseline (Appendix 2.2.4): Only participants with baseline PP-NRS ≥4 in the FAS are included in all analyses of this endpoint.
- ≥4-point reduction in Skin Pain NRS score from baseline (Appendix 2.2.5): Only participants with baseline Skin Pain NRS ≥4 in the FAS are included in all analyses of this endpoint.
- ≥4-point reduction in POEM from baseline (Appendix 2.2.6): Only participants with baseline POEM ≥4 in the FAS are included in all analyses of this endpoint.

For all other efficacy endpoints, the general rule of including the complete FAS still applies.

